5.0 Inclusion and Exclusion Criteria/ Study Population

Inclusion Criteria

- Healthy adults with no known chronic medical conditions between the ages of 18 and 60 years old willing and able to consent themselves.
- Subjects who are native English speakers or self-report as fluent in English.

Exclusion Criteria

- Subjects who have a history of or are a current smoker, have a history of or current illicit drug use, have a history of or current alcohol abuse.
- Subjects who self-report as pregnant.

- Subjects who self-report diabetes, cardiac disease including hypertension requiring medication, or a history of compartment syndrome or peripheral vascular disease.
- Subjects with known chronic diseases not listed above, including but not limited to Rheumatoid Arthritis, McArdle's disease, etc.
- Subjects with elevated blood pressure (>130/80mmHg) on the day of the study

6.0 Number of Subjects

- A total of 30 healthy volunteered adults (15 males and 15 females) will be used for our study.
- A power analysis was conducted to determine appropriate sample sizes based on previous data examining hemodynamics following tourniquet application on the lower extremities²¹. Based on a power of 0.8 and an alpha of 0.05, a sample size of 24 participants will be needed for our study. Allowing for post hoc analysis and individual data exclusion if warranted, a total of 30 volunteer research participants will be recruited to partake in the study.

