4.0 Study Endpoints (if applicable)

- **Primary Study Endpoint:** A cardiac arrest porcine model that utilized an intra-aortic balloon catheter for occlusion of the aorta at the level of the diaphragm demonstrated a mean increase in systolic pressure of 17mmHg.¹⁸ Extrapolating from this data to our more distal point of occlusion at the lower extremities, we define the primary study endpoint as successful application of CAT tourniquets in normal physiology in healthy humans with a minimum increase in blood pressure of 10 mmHg measured in the arms. Another primary endpoint is demonstrating no significant change in participant heart rate.
- **Primary Safety Endpoint:** The most common complications following application of a CAT tourniquet is pain or discomfort at the site of tourniquet application. This usually occurs at the edges of the tourniquet due to the increased pressure gradient. Symptoms are typically transient resulting in mild to moderate pain. In order to increase safety of the study and reduce the likelihood of complications, the tourniquet will be tightened to the minimum pressure needed to occlude blood flow to the lower extremities and will be removed after 5 minutes since injury usually occurs 30-60 minutes following tourniquet application²⁰. If any of the subjects report intolerable pain during the study, their participation will be ended immediately.
- **Secondary Safety Endpoints:** There are no secondary safety endpoints.

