10.0 Study Design / Methods

After expressing interest in the study, participants will be asked to come to MUSC for the study visit. On the day of the study, each volunteer will be taken to a private room by IRB approved personnel and consented in person through a signed written consent form. They will be asked to confirm their eligibility in the study based on the inclusion/exclusion criteria. Their blood pressure in their upper extremity will be taken to ensure that it is not elevated on the day of the study (must not be $>130/80$ mmHg). Their responses and blood pressure will be documented. Once the participants have consented to the study, they will have their height and weight recorded. Then, each participant will have their blood pressure measured in each arm by an automated sphygmomanometer while lying down on a medical bench. The blood pressures and the heart rate will be recorded by IRB approved personnel. This will allow each research participant to act as their own control for the experimental procedure. Then, one CAT tourniquet will be placed around each thigh and tightened until no pulse can be felt in the lower extremity. Blood pressure measurements will be repeated in each arm once the tourniquets are secured. Once these blood pressures are documented, the tourniquets will be removed. The maximum time the tourniquets will be applied is 5 minutes to ensure ample time for blood pressure recording. If the measurement cannot be taken within the time frame, the tourniquets will be released. The participants will rest 3-5 minutes between each repetition of the tourniquet application. The whole process will be repeated three times for data validity. CAT tourniquets have been extensively studied for safety, and no long-term consequences or complications have been noted for up to two hours of continuous use. This team will prioritize the safety and comfort of the participant and will limit the tourniquet application time to a maximum of 5 minutes. We will be using the FDA-approved Combat Application Tourniquet (CAT) tourniquet (North American Rescue, Greer, South Carolina, USA). After the data is collected, a debrief session will be conducted, allowing for additional subject monitoring after removal of the tourniquets. During the debrief session, the participant will be asked to lay down or sit in a relaxed position for 5 minutes or until they feel that their leg function is back to baseline. If there is any concern from the participant, the PI or IRB-approved personnel who are medical doctors, will conduct an evaluation. If any of the safety endpoints are noted, it will be recorded, and the participant will be taken to the emergency room for full examination and work-up. The PI or IRB-approved personnel will follow-up with the participant remotely until the safety concern is resolved.

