12.0 Withdrawal of Subjects

- Research subjects may refuse to participate or stop participating in the study at any time by notifying the principal investigator or approved IRB personnel.
- If research participants would like to have their data removed from the study, they must notify the principal investigator in writing within a week of completing the study.

- If the principal investigator or approved IRB personnel determine that participation in the study is not in the best interest of the research subject, they may remove the research participant from the study.

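### Does the allowance for excluding individual data in the sample-size section open the way to dropping participants after their readings are known?

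*Protocol*

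**What the plan says.** Protocol section 6.0 states: "Based on a power of 0.8 and an alpha of 0.05, a sample size of 24 participants will be needed for our study". The calculation is said to be "based on previous data examining hemodynamics following tourniquet application on the lower extremities", but neither the effect nor the standard deviation is given. The next sentence raises the number: "Allowing for post hoc analysis and individual data exclusion if warranted, a total of 30 volunteer research participants will be recruited". Two reasons are therefore given for the surplus, later analyses and exclusions, and neither is elaborated.

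The primary endpoint in section 4.0 is successful tourniquet application "with a minimum increase in blood pressure of 10 mmHg measured in the arms", together with no significant change in heart rate.

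Other sections describe how data may be lost:
- Section 4.0 ends participation for intolerable pain.
- Section 10.0 covers a reading not obtained in time: "If the measurement cannot be taken within the time frame, the tourniquets will be released".
- Section 12.0 covers removal of data on request: "If research participants would like to have their data removed from the study, they must notify the principal investigator in writing". It also lets the investigator take a participant out in that person's interest.
- Section 13.0 stops testing after pain or injury at the tourniquet site.

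**The concern.** Section 6.0 does not say what justifies an exclusion, who decides, or whether the decision precedes knowledge of the readings. It does not link the surplus to the data-loss routes named elsewhere. Each person is their own control and study personnel record both readings, so the change is visible at once.

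If people were removed because of that change, two things would suffer. The 0.05 significance level would no longer hold, and the mean change would move relative to the 10 mmHg criterion. Removing low responders would push it upward. Losses unrelated to the response do neither, and the sentence does not separate the two kinds.

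**Working it through.** **Inputs from section 6.0.** Power 0.8, alpha 0.05, 24 required, 30 recruited.

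**The plan's own figures.** The 24 cannot be recomputed, because no effect size, standard deviation, test or sidedness is given. Solving backwards with a two-sided paired t-test, n = 24 and 80% power imply a standardised mean change of 0.597. If the planning effect were 10 mmHg (an assumption, since section 6.0 does not say so), the SD of the change would be 10 / 0.597 = 16.7 mmHg. The surplus is 30 − 24 = 6, and 6 / 30 = 20%. So 30 also equals 24 / (1 − 0.20), although the protocol states no loss rate.

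**Simulation.** 200,000 data sets of 30 normal changes with no true effect, tested by a one-sample t-test against zero. The protocol does not name this test.

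| Exclusion rule | Error rate |
|---|---|
| Outcome-independent loss of 1, 3 or 6 | two-sided about 5% |
| Drop beyond 2 SD of the sample mean | two-sided 10.3% (someone dropped in 82% of trials) |
| Drop beyond 2.5 SD | two-sided 6.7% (25% of trials) |
| Drop beyond 3 SD | two-sided 5.3% (3% of trials) |
| Drop the lowest 1 | upper tail 6.7% (nominal 2.5%) |
| Drop the lowest 3 | upper tail 21.7% (nominal 2.5%) |
| Drop the lowest 6 | two-sided 53.5% |

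**Effect on the 10 mmHg criterion.** Dropping the lowest 1 or 3 raises the mean by 0.071 or 0.186 SD.
- At an assumed SD of 10 mmHg: 0.071 × 10 = 0.7 and 0.186 × 10 = 1.9 mmHg.
- At SD 16.7 mmHg: 0.071 × 16.7 = 1.2 and 0.186 × 16.7 = 3.1 mmHg.

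With no true effect and SD 16.7, the mean reaches 10 mmHg in 0.05%, 0.19% and 1.3% of trials with 0, 1 and 3 people dropped. At SD 10 it does so in under 0.01% of trials in each case. On this criterion the bias would matter mainly if the true rise were close to 10 mmHg.

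**Which row describes the plan.** Only the first row can be tied to anything in the text. Withdrawal of data on request, removal in the participant's interest and a reading not obtained in time are not decisions taken on the size of the blood-pressure change. Strict independence from the response is an assumption for some of them, such as stopping for pain. No outlier rule or selection of low responders appears anywhere in the protocol.

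**The case for a change.** The best case for a change is that this is more than a missing detail. The protocol itself reserves people for discretionary exclusion and uses that to justify its sample size, so an analysis plan could narrow the sentence but would not erase it. Harm needs no bad faith, because a familiar 2 SD rule applied after looking at the data doubles the error rate. The automated cuff protects the readings, but not the decision about whose readings count. A clarification would take a few sentences and no extra participants.

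Much of this stands. The wording is open, no other section closes it, and the simulated figures are right for the rules they describe.

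The step from loose wording to a defect does not stand. The sentence sits under the number of subjects and explains recruitment. It does not define who is analysed. It requires that an exclusion be justified, and it does not authorise exclusion by response. What counts as justified is the kind of detail commonly left to the analysis plan. A hurried rule in the protocol could also do harm. One that admitted only technical faults logged at measurement would keep in the primary analysis people later found ineligible under section 5.0. It would also leave unclear what happens to an application that failed to abolish the pulse, as section 10.0 requires.

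**Conclusion.** No change to the protocol is needed. Section 6.0 is loosely worded, but it states a recruitment margin of 6 over 24. It does not permit exclusion by outcome. If exclusions follow the routes the protocol names and are unrelated to the response, the error rate stays at about 5% even when all 6 surplus participants are lost.

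The larger figures, 10.3% for a 2 SD rule and 21.7% for dropping the three lowest, illustrate hypothetical rules and are not properties of this plan. They also assume a test against zero. The shifts in mmHg rest on assumed SDs of 10 and 16.7.

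The conclusion supposes that the analysts set grounds for exclusion that do not depend on the observed blood-pressure or heart-rate change: ineligibility, device error, no valid reading, occlusion not achieved, or data removed on request. Any other exclusion would be shown only as a sensitivity analysis. That is ordinary practice, and an analysis plan not shown here may already provide for it.

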7.0 Setting

- Study participants will meet in a private conference room at MUSC where the research protocol will be completed.

Study Sites

- MUSC

8.0 Recruitment Methods

- Flyers will be displayed around the MUSC campus in order to recruit subjects voluntarily (Copy of flyer attached to IRB application).
- Volunteers will be screened via a phone call to determine their eligibility for the study and will be asked questions related to the exclusion criteria in order to identify potential subjects.

9.0 Consent Process

- IRB approved personnel will obtain voluntary informed consent for all research participants.
- Volunteers that were identified as potential subjects based on inclusion and exclusion criteria will be informed of the study procedures over the phone prior to participation in the study.
- Participants will be consented the day of the study in a private room by IRB approved personnel prior to beginning the study. This will be conducted in person through a signed written consent form. Participants will have ample time to read the consent form and ask questions to IRB approved personnel.
- Participants may refuse to take part in the study or stop taking part in the study at any time by notifying the study investigator or approved IRB personnel.
- There will be no cost nor compensation for participating in the study to avoid undue influence or coercion of study participants.

10.0 Study Design / Methods

After expressing interest in the study, participants will be asked to come to MUSC for the study visit. On the day of the study, each volunteer will be taken to a private room by IRB approved personnel and consented in person through a signed written consent form. They will be asked to confirm their eligibility in the study based on the inclusion/exclusion criteria. Their blood pressure in their upper extremity will be taken to ensure that it is not elevated on the day of the study (must not be $>130/80$ mmHg). Their responses and blood pressure will be documented. Once the participants have consented to the study, they will have their height and weight recorded. Then, each participant will have their blood pressure measured in each arm by an automated sphygmomanometer while lying down on a medical bench. The blood pressures and the heart rate will be recorded by IRB approved personnel. This will allow each research participant to act as their own control for the experimental procedure. Then, one CAT tourniquet will be placed around each thigh and tightened until no pulse can be felt in the lower extremity. Blood pressure measurements will be repeated in each arm once the tourniquets are secured. Once these blood pressures are documented, the tourniquets will be removed. The maximum time the tourniquets will be applied is 5 minutes to ensure ample time for blood pressure recording. If the measurement cannot be taken within the time frame, the tourniquets will be released. The participants will rest 3-5 minutes between each repetition of the tourniquet application. The whole process will be repeated three times for data validity. CAT tourniquets have been extensively studied for safety, and no long-term consequences or complications have been noted for up to two hours of continuous use. This team will prioritize the safety and comfort of the participant and will limit the tourniquet application time to a maximum of 5 minutes. We will be using the FDA-approved Combat Application Tourniquet (CAT) tourniquet (North American Rescue, Greer, South Carolina, USA). After the data is collected, a debrief session will be conducted, allowing for additional subject monitoring after removal of the tourniquets. During the debrief session, the participant will be asked to lay down or sit in a relaxed position for 5 minutes or until they feel that their leg function is back to baseline. If there is any concern from the participant, the PI or IRB-approved personnel who are medical doctors, will conduct an evaluation. If any of the safety endpoints are noted, it will be recorded, and the participant will be taken to the emergency room for full examination and work-up. The PI or IRB-approved personnel will follow-up with the participant remotely until the safety concern is resolved.

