2.0 Intervention to be studied

The fluid dynamics Hagen-Poiseuille Equation demonstrates in physical law why peripheral vasoconstriction increases the flow in conserved vascular networks. The Hagen-Poiseuille Equation ($Q = \Delta P \pi r^4 / 8 \eta L$) gives the volumetric flow rate (Q) in a cylindrical tube as it relates to the viscosity of the fluid (η), length of the system (L), radius of the tube (r), and pressure gradient across the tubing (ΔP). Tourniquets placed on the legs would decrease the length of the system (L), thereby increasing the flow (Q) as these variables are inversely proportional. While this equation is an obvious oversimplification, we find it models our expectant results and confirms what we intuitively and anecdotally have noted in our patients. Beyond theory, studies in large animal models and clinical trials offer additional proof of concept.^{4,12-13,15-19} Pigs receiving tourniquet-assisted CPR experienced significantly increased coronary blood flow,

carotid artery pressure, systolic and diastolic blood pressure, end-tidal carbon dioxide, and survival than controls.¹⁷

In order to complete our hypothesis testing safely, we plan to deploy well-studied and FDA approved combat application tourniquets (CAT) on both thighs of volunteer healthy adult subjects while measuring blood pressure in the upper extremities. Research participants in this study will have their blood pressure measured in their upper extremities before and after tourniquet administration in order to serve as within subject controls. The tourniquets will be deployed for no longer than 5 minutes for each of the three repetitions. After the removal of the tourniquets, the participants will be allowed to rest for 3-5 minutes before the next application of the tourniquet.

CAT tourniquets were developed in 2005 by Mark Esposito et al. (US Patent numbers 7,842,067 and 7,892,253) and soon after obtained FDA approval. CAT tourniquets have been indicated for use in emergency situations revolving around a wounded limb, such as hemorrhage control.²²⁻²³ CAT tourniquets are the official tourniquet of the US Army since in 2005.

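### Section 10.0 sets no rest before the first control reading but rest before each later application, so settling can be counted as tourniquet effect in both primary endpoints

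*Protocol*

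**What the plan says.** Protocol section 10.0 gives the order of the visit. Consent and confirmation of eligibility come first, with a screening pressure in the upper extremity. Next, "Once the participants have consented to the study, they will have their height and weight recorded". The control reading follows: "Then, each participant will have their blood pressure measured in each arm by an automated sphygmomanometer while lying down on a medical bench". Heart rate is taken at that point too: "The blood pressures and the heart rate will be recorded by IRB approved personnel". The purpose of the reading is explicit: "This will allow each research participant to act as their own control for the experimental procedure". The thigh tourniquets are then tightened and the arm pressures repeated.

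Rest is specified only from the second application onward. Section 10.0 says "The participants will rest 3-5 minutes between each repetition of the tourniquet application", and the section on the intervention says "After the removal of the tourniquets, the participants will be allowed to rest for 3-5 minutes before the next application of the tourniquet". Section 10.0 also states: "The whole process will be repeated three times for data validity".

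Section 4.0 names two primary endpoints measured by this before-and-after comparison. One is a rise of at least 10 mmHg in arm pressure. The other concerns heart rate: "Another primary endpoint is demonstrating no significant change in participant heart rate".

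**The concern.** Weighing, measuring height and lying down come just before the first control reading, and pressure and heart rate may still be falling when it is taken. The tourniquet reading comes a little later. With no sham or tourniquet-free period, the design cannot separate a fall due to settling from an effect of the tourniquets.

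The later applications are preceded by a specified rest, so the three within-subject comparisons may not be made under like conditions. The two endpoints are affected differently:

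- **Pressure.** A control that is too high is subtracted from the tourniquet reading, so the apparent rise is too small when set against a fixed 10 mmHg.
- **Heart rate.** The endpoint is met by finding no significant change. A control that is too high can mask a true rise, which favours the endpoint. If there is no true change, it can produce an apparent fall, which counts against it.

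Measurement conditions belong in the protocol's methods. A later analysis cannot reliably tell settling from a genuinely different first application.

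**Working it through.** **1. Sequence.** Set side by side, section 10.0 and the intervention section give a rest before applications 2 and 3 and none before the first control. No other section supplies one.

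**2. How drift enters the estimate.** Let the first control be too high by d, and the other controls be settled.

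- Application 1: apparent change = true change − d.
- Mean of three applications: apparent change = true change − d/3.
- If only one baseline serves all three applications: apparent change = true change − d throughout.

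**3. The plan's own figure.** Section 6.0 states power 0.8, alpha 0.05 and 24 participants, with 30 recruited. It gives no effect size, SD or sidedness, so 24 cannot be reproduced forwards. Solved backwards with a two-sided paired t-test (noncentral t, 23 degrees of freedom), power 0.80 at n=24 needs a standardised change of 0.597. If the target was 10 mmHg, the SD of change is 10/0.597 = 16.7 mmHg. That target is an assumption.

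**4. Pressure (illustration).** The true rise is 10 mmHg, the SD 16.7 mmHg, and the test is two-sided against zero at 0.05. The values of d are assumed.

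| d (mmHg) | Mean of three, 10 − d/3 | Standardised | Power, n=24 | Power, n=30 |
|---|---|---|---|---|
| 0 | 10.0 | 0.597 | 0.80 | 0.89 |
| 3 | 9.0 | 0.537 | 0.71 | 0.81 |
| 5 | 8.3 | 0.498 | 0.65 | 0.75 |
| 8 | 7.3 | 0.438 | 0.54 | 0.64 |

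For application 1 alone, the apparent rise is 7, 5 or 2 mmHg for d = 3, 5 or 8.

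**5. Heart rate (illustration).** Assumed: SD of change 5 bpm, n=30, settling 2 bpm in the first control only. The probability of a non-significant result is 1 − power at (true change − shift)/5, where the shift is 2/3 bpm for the mean of three and 2 bpm for application 1.

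| True change | No settling | Mean of three | Application 1 alone |
|---|---|---|---|
| +3 bpm | 0.11 (3/5 = 0.600) | 0.30 (2.33/5 = 0.467) | 0.81 (1/5 = 0.200) |
| 0 bpm | 0.95 | 0.89 (−0.67/5 = −0.133) | 0.44 (−2/5 = −0.400) |

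The first row is a true rise being missed. The second is a spurious fall being declared.

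**The case against.** The strongest reply is that the text is silent rather than wrong. A reader might infer that participants get no rest and that settling does distort the results. The protocol supports neither inference. It states no interval between lying down and the first reading, staff may allow one, and no settling size is given. What stands is that no rest is required and that settling can bias the result.

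A second inference is that the later controls are known to be rested. Separate controls for applications 2 and 3 follow only from reading the repeated process as including the control reading. The rest is placed between applications, and when a control is taken within it is not stated. This limits how firmly the contrast can be drawn. It gives no reassurance, since a single unrested baseline would carry the full drift into every application.

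Third, one might conclude that settling makes the heart-rate endpoint easier to meet. That holds only if there is a true rise. Section 1.0 expects no substantial change, and in that case settling makes the endpoint harder to meet. Section 10.0 also names only blood pressure as repeated with the tourniquets on, so the timing of the comparison heart rate is itself unstated. A rest period would not cure the separate weakness of treating non-significance as evidence of no change.

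Fourth, the pressure figures may overstate the loss.

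- With all 30 analysed, 3 mmHg of settling still leaves power at 0.81, above the planned 0.8.
- The 16.7 mmHg SD is inferred. If it describes a single application, and a correlation of 0.5 between applications is assumed, the SD of the mean is 16.75 × √(2/3) = 13.7 mmHg. Power at n=30 is then 0.94, 0.90 and 0.81 for 3, 5 and 8 mmHg.
- The test is against zero, while section 4.0 asks for a rise of at least 10 mmHg.

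Finally, downward settling cannot manufacture a false pressure success. All of this stands and limits the severity. It does not remove the shift in the estimated rise, which extra participants and averaging of random error leave unchanged.

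**Conclusion.** The concern holds as a gap in the measurement procedure, at low-to-moderate severity. No rest is specified before the first control, rest is specified before later applications, and a purely before-and-after design has nothing with which to separate settling from effect.

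Downward settling can understate the first-application pressure rise by its full size and a three-application mean by one third of it, or every application in full if there is only one baseline. It can move the heart-rate result either way, so that endpoint is not measured cleanly whether or not a true rise exists.

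The direction of the pressure bias and the one-third rule follow from the design once downward settling in the first control is supposed. The power and probability figures are illustrations. They rest on assumed settling of 3 to 8 mmHg and 2 bpm, an assumed heart-rate SD of 5 bpm, and a pressure SD that is correct only if 24 participants were sized on a 10 mmHg rise with a two-sided test.

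**What to change.** In section 10.0:

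- Add a supine rest between lying down and the first control reading.
- Choose one fixed duration within the 3-5 minute range already in the protocol, and use it before every control reading, including the first.
- State that each application has its own control, and that control pressure and heart rate are both taken at the end of that rest, before the tourniquets are tightened.

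This changes only the conditions of measurement. It costs a few minutes per participant and a sentence or two of text, with no added participants, staff or equipment.

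### The control reading comes before strap placement, so the before-after change includes any response to placement and handling as well as occlusion

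*Protocol*

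**What the plan says.** Section 10.0 (Study Design / Methods) fixes the order of events within a repetition. The control comes first: "Then, each participant will have their blood pressure measured in each arm by an automated sphygmomanometer while lying down on a medical bench". Heart rate is recorded with it. The section gives the role of this reading: "This will allow each research participant to act as their own control for the experimental procedure". The intervention follows as one step: "Then, one CAT tourniquet will be placed around each thigh and tightened until no pulse can be felt in the lower extremity". Then come the on-tourniquet readings and release: "Blood pressure measurements will be repeated in each arm once the tourniquets are secured" and "Once these blood pressures are documented, the tourniquets will be removed".

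The section headed 2.0 Intervention to be studied describes the same contrast, with pressures taken "before and after tourniquet administration in order to serve as within subject controls". It also gives the number of cycles and the time limit: "The tourniquets will be deployed for no longer than 5 minutes for each of the three repetitions". Section 10.0 adds "The whole process will be repeated three times for data validity", with 3 to 5 minutes of rest between repetitions. After the third release it describes a debrief with about 5 minutes of rest, lying or sitting, and names no pressure or heart-rate reading.

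Section 1.0 states the aim as showing that peripheral vascular occlusion raises pressure. Section 4.0 sets a minimum rise of 10 mmHg in the arms and, as another primary endpoint, no significant change in heart rate.

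**The concern.** The only control in this study is the participant's own earlier reading. A before-after contrast isolates occlusion only if occlusion is the sole thing that changes between the two readings. Here a conscious volunteer also has a strap fitted to each thigh, with the handling that this involves. Any response to that is counted as an occlusion effect on pressure, and it also enters the heart-rate comparison.

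The study is meant as proof of concept for a device used in cardiac arrest, where a conscious response to handling would not be expected. A change that partly reflects placement would therefore not carry over. The measurement schedule is set in the protocol itself, and no analysis plan can recover a loose-strap reading that was never taken.

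**Working it through.** **Inputs.** The order of readings is from Section 10.0, the three repetitions from 2.0 Intervention to be studied, the 10 mmHg criterion from Section 4.0, and N = 24 needed and 30 recruited from Section 6.0. The size of a placement response, the SD of the change and the sidedness of alpha are not stated anywhere.

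**Step 1: what the contrast contains.** Let θ be the occlusion effect, p the response to placement and handling, t the response to the pain or anticipation of tightening, and c any excess in the control reading because the participant has not settled. With μ the resting level:

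- As planned: control = μ + c; on-tourniquet = μ + θ + p + t; change = θ + p + t − c.
- Straps placed loose first, then settling, then control: control = μ + c′ + p; on-tourniquet = μ + θ + p + t; change = θ + t − c′, where c′ is whatever excess remains after settling.

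If p persists, it is in both readings and cancels. If it fades during settling, it is in neither. The term t stays in both designs.

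**Step 2: repetition.** The mean of three changes is θ plus the mean of (p + t − c) over the repetitions. Averaging reduces random error but not this term, because each repetition follows the same order and the straps are removed in between.

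**Step 3: possible size.** Leave t aside and write b = p − c. The documents give no value, so assume −5 to +5 mmHg, a range that includes zero and both signs. Recorded change = θ + b. With θ = 10 this gives 10 − 5 = 5 up to 10 + 5 = 15 mmHg. Conversely, a recorded 10 mmHg could come from a θ of 10 − 5 = 5 up to 10 + 5 = 15 mmHg.

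**Step 4: effect on a test of zero change.** The stated N = 24 cannot be reproduced, because the effect size, SD, test and sidedness are not given. Back-solving a paired t-test at two-sided 0.05 and 80% power gives a standardised change of 0.597, which implies an SD of 10/0.597 ≈ 16.7 mmHg if the target is 10 mmHg. One-sided, it gives 0.523 and 10/0.523 ≈ 19.1 mmHg.

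Now set θ = 0 and n = 30, two-sided 0.05. The rejection rate comes from the noncentral t with 29 degrees of freedom and noncentrality b√30/SD. For example, b = 3 and SD = 12 give 3 × 5.477/12 = 1.37 and a rate of 26%.

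| Assumed SD (mmHg) | b = 2 | b = 3 | b = 5 |
|---|---|---|---|
| 8 | 26% | 51% | 91% |
| 12 | 14% | 26% | 60% |
| 16.7 | 10% | 16% | 35% |

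The nominal rate is 5%. A negative b gives the same rates, mostly in the direction of a fall. These rates concern a null of zero change, not the 10 mmHg criterion. With θ = 0 the expected recorded change is b, at most 5 mmHg in this range and so short of 10.

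**Step 5: readings after release.** If the whole process includes the control reading, which is the natural meaning but is not spelled out, the controls for repetitions 2 and 3 also serve as readings after releases 1 and 2. Release 3 has none. Under a linear drift of d per reading step, the six planned readings (control, on, control, on, control, on) carry 0, d, 2d, 3d, 4d, 5d. On minus preceding control is then biased by d in every repetition. One more off reading after the third release would give a further point for seeing such drift.

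**The case against.** The strongest reply is that nothing here is shown to be wrong. The documents give no handling effect, and Section 10.0 says nothing about lifting or moving the legs. A reader might infer that the bias favours reaching 10 mmHg, but the text does not support a direction. The first control follows consent, a screening pressure and height and weight, with no settling period stated, so it may itself be raised and shrink the recorded change. Nor can placement alone be said to meet the criterion: with no occlusion effect, a shift of 2 to 5 mmHg stays below 10. If handling raised heart rate as well, it would count against the heart-rate endpoint, which is a partial safeguard. All of this stands, and it limits the point to a risk of unknown sign and size.

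The remedy is also partial. Section 4.0 names pain or discomfort at the site as the most common complication, and loose straps do not remove a response to it. That stands too, but it is no reason to leave in a second difference that can be taken out by reordering.

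A reader might also infer that the missing reading after the third release is a defect in its own right, or that each on-tourniquet reading should be compared with the mean of the off readings on either side. No endpoint concerns return to baseline, so the first inference goes too far. On the second, averaging in a reading taken after release can carry over an after-effect of the tourniquet. It would do so even in repetition 1, the only repetition whose control precedes any tourniquet. A debrief reading might also be taken seated, against controls taken lying down.

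**Conclusion.** The concern holds as a risk of bias. The planned contrast measures occlusion plus any response to placement and handling, while the protocol attributes the whole change to occlusion. This follows from the stated order of steps and needs no assumed number. How much it matters cannot be settled from the documents. The range of 5 to 15 mmHg recorded for a true 10, and the rejection rates of 10% to 91% in place of 5%, rest on assumed shifts and SDs and are illustrations only. The point is a worthwhile low-cost improvement to a small proof-of-concept study, not a demonstrated error. The lack of a reading after the third release is a lesser matter, useful for description only.

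**What to change.** In Section 10.0, for each of the three repetitions:

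- Place both tourniquets untightened with the participant lying down and let the participant settle.
- Take the control pressures in both arms and the heart rate.
- Tighten, then repeat the same readings, naming heart rate as well as pressure.
- State explicitly that the control reading is repeated in every repetition.

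Keep the primary contrast as on-tourniquet minus the preceding control, and do not use a mean of bracketing readings. Optionally, add one set of off-tourniquet readings after the third release, lying down and at the same 3 to 5 minute interval as the earlier rests, as a descriptive check of drift or return to baseline.

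The 5-minute limit appears in 2.0 Intervention to be studied, in Section 10.0 and in Section 13.0 without saying whether time with untightened straps counts. The protocol should say so, and the passages should be made consistent.

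The cost is one to two more minutes per visit. The response to pain or anticipation of tightening is not removed and should be written down as a limitation.
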